# 2.8 Safety analyses

Safety analyses for Part 1 and Part 2 will be based on SAF1 and SAF2, respectively. All listings and tables will be presented by treatment group.

Safety analyses will be based on ESS1 and will be presented by dosing posology (TID and BID). The reporting will include all the data from

until the end of the study. The baseline value for all safety endpoints in ESS1 is the last available value collected prior to or on the first administration

The safety analysis will consist of descriptive summaries. Continuous variables will be presented with n, mean, standard deviation, median, minimum and maximum. Categorical data will be displayed with frequency and percentage.

Adeverse Events will be reported at subject level and other safety endpoints will be reported for each eye.

# 2.8.1 Adverse events (AEs)

In Part 1, AEs will be summarized for TEAE, pre-treatment AE and post-treatment AE separately.

- 1. Pre-treatment AEs are adverse events started between ICF signature and prior to the first administration of randomized study treatment.
- 2. Treatment emergent adverse events (TEAEs) are adverse events started after the first administration of randomized study treatment or events present prior to start of the randomized treatment but increased in severity based on preferred term.
- 3. Post-treatment AEs are adverse events started after the last administration of randomized study treatment to the end of the study.

For Part 1 and Part 2, the number (and percentage) of subjects with AEs will be summarized for ocular and non-ocular respectively, by treatment, in the following ways:

- primary system organ class and preferred term.
- primary system organ class, preferred term and maximum severity.
- Standardized MedDRA Query (SMQ) and preferred term.

Separate summaries for TEAEs will be provided for study medication related AEs, death, serious adverse events (SAE), other significant AEs leading to discontinuation.

For ESS1, the number (and percentage) of subjects with AEs will be summarized for ocular and non-ocular respectively, by dosing posology (TID and BID) in the following ways:

- primary system organ class and preferred term.
- primary system organ class, preferred term and maximum severity.
- Standardized MedDRA Query (SMQ) and preferred term.

A subject with multiple adverse events within a primary system organ class is only counted once towards the total of the primary system organ class. All these analyses will be based on the most updated MedDRA version available prior to the database lock.

All adverse events reporting will be included in the subject listings respectively.

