10.1 Definition of adverse events and reporting requirements

10.1.1 Adverse events

An adverse event (AE) is any untoward medical occurrence (e.g., any unfavorable and unintended sign [including abnormal laboratory findings], symptom or disease) in a subject or clinical investigation subject after providing written informed consent for participation in the study. Therefore, an AE may or may not be temporally or causally associated with the use of a medicinal (investigational) product.

The investigator has the responsibility for managing the safety of individual subject and identifying adverse events.

Novartis qualified medical personnel will be readily available to advise on trial related medical questions or problems.

The occurrence of adverse events must be sought by non-directive questioning of the subject at each visit during the study. Adverse events also may be detected when they are volunteered by the subject during or between visits or through physical examination findings, laboratory test findings, or other assessments.

Adverse events must be recorded under the signs, symptoms, or diagnosis associated with them, accompanied by the following information (as far as possible) (if the event is serious refer to Section 10.1.2):

- 1. Severity grade
- mild: usually transient in nature and generally not interfering with normal activities
- moderate: sufficiently discomforting to interfere with normal activities
- severe: prevents normal activities
- 2. its relationship to the study treatment (i.e., blinded study medication [ECF843 vs Vehicle], as applicable). If the event is due to lack of efficacy or progression of underlying illness (i.e. progression of the study indication) the assessment of causality will usually be 'Not suspected'. The rationale for this guidance is that the symptoms of a lack of efficacy or progression of underlying illness are not caused by the trial drug, they happen in spite of its administration and/or both lack of efficacy and progression of underlying disease can only be evaluated meaningfully by an analysis of cohorts, not on a single subject
- 3. its duration (start and end dates) or if the event is ongoing, an outcome of not recovered/not resolved must be reported
- 4. whether it constitutes a SAE (see Section 10.1.2 for definition of SAE) and which seriousness criteria have been met
- 5. action taken regarding with study treatment (i.e., blinded study medication [ECF843 vs Vehicle], as applicable)
- 6. its outcome

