12.5.2 Safety endpoints

Safety analysis for Part 1 and Part 2 will be performed separately, based on respective safety set. All listings and tables will be presented by treatment group.

The safety analysis will consist of descriptive summaries. Continuous variables will be presented with n, mean, standard deviation, median, minimum and maximum. Categorical data will be displayed with frequency and percentage.

Adverse events

All information obtained on adverse events (ocular and non-ocular), will be displayed by treatment group and subject.

The number (and percentage) of subjects with treatment emergent adverse events (events started after the first dose of study medication or events present prior to start of double-blind treatment but increased in severity based on preferred term) will be summarized in the following ways:

- by treatment, primary system organ class and preferred term.
- by treatment, primary system organ class, preferred term and maximum severity.
- by treatment, Standardized MedDRA Query (SMQ) and preferred term.

Separate summaries will be provided for study medication related adverse events, death, serious adverse events, other significant adverse events leading to discontinuation.

The number (and proportion) of subjects with adverse events of special interest/related to identified and potential risks will be summarized by treatment.

A subject with multiple adverse events within a primary system organ class is only counted once towards the total of the primary system organ class.

Adverse events which will be counted for a specific treatment period are those which are treatment-emergent. These events are those with an onset after the start of the treatment period, or which were present prior to the start of the treatment period but increased in severity, changed from being not suspected to being suspected of study drug relationship, or developed into SAEs after the start of the treatment period.

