# 4 Change to protocol specified analyses

The following analyses are updated and changed from protocol amendment version 1 dated 20 Apr 2021.

1. Section 2.5.2 Statistical hypothesis, model, and method of analysis: The initial within subject correlation structure used for SANDE symptom score in MMRM is updated from "Unstructured" to "Toeplitz". This also applies to the supportive analysis for SANDE symptom score stated in 2.5.4 Supportive analyses.

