#### 5.1.1.2 Adverse event start date imputation

The following table explains the notation used in the logic matrix. Please note that **missing start dates** will not be imputed.

	Day	Month	Year
Partial Adverse Event Start Date	Not used	MON	YYYY
Treatment Start Date	Not used	TRTM	TRTY

The following matrix explains the logic behind the imputation.

	MON MISSING	MON < TRTM	MON = TRTM	MON > TRTM
YYYY	(1)	(1)	(1)	(1)
MISSING	No convention	No convention	No convention	No convention
YYYY < TRTY	( 2.a )	( 2.b )	( 2.b )	( 2.b )
	Before Treatment	Before Treatment	Before Treatment	Before Treatment
	Start	Start	Start	Start
YYYY = TRTY	( 4.a ) Uncertain	( 4.b ) Before Treatment Start	( 4.c ) Uncertain	( 4.c ) After Treatment Start
YYYY > TRTY	( 3.a )	( 3.b )	( 3.b )	( 3.b )
	After Treatment Start	After Treatment Start	After Treatment Start	After Treatment Start

Before imputing AE start date, find the AE start reference date.

- 1. If the (imputed) AE end date is complete and the (imputed) AE end date < treatment start date then AE start reference date = min (informed consent date, earliest visit date).
- 2. Else AE start reference date = treatment start date

Impute AE start date

- 1. If the AE start date year value is missing, the date uncertainty is too high to impute a rational date. Therefore, if the AE year value is missing, the imputed AE start date is set to NULL.
- 2. If the AE start date year value is less than the treatment start date year value, the AE started before treatment. Therefore:
  - a. If AE month is missing, the imputed AE start date is set to the mid-year point (01JulYYYY).
  - b. Else if AE month is not missing, the imputed AE start date is set to the mid-month point (15MONYYYY).
- 3. If the AE start date year value is greater than the treatment start date year value, the AE started after treatment. Therefore:
  - a. If the AE month is missing, the imputed AE start date is set to the year start point (01JanYYYY).
  - b. Else if the AE month is not missing, the imputed AE start date is set to the later of (month start point (01MONYYYY), AE start reference date + 1 day).
- 4. If the AE start date year value is equal to the treatment start date year value:
  - a. And the AE month is missing the imputed AE start date is set to the AE reference start date + 1 day.

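### Protocol 12.5.2 defines treatment-emergent events in two ways and SAP 2.8.1 implements only the narrower, so pre-existing events that turn serious or suspected are missing from the drug-related and SAE tables

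*SAP*

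**What the plan says.** Protocol 12.5.2 describes treatment-emergent adverse events twice.

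- The paragraph introducing the summary tables counts "events started after the first dose of study medication or events present prior to start of double-blind treatment but increased in severity".
- The closing paragraph, on events counted for a specific treatment period, takes onset after the start of that period or increased severity, and adds events that "changed from being not suspected to being suspected of study drug relationship, or developed into SAEs after the start of the treatment period".

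SAP 2.8.1 gives one rule for Part 1, with two conditions. The first concerns onset: "Treatment emergent adverse events (TEAEs) are adverse events started after the first administration of randomized study treatment". The second deals with anything that had begun earlier, and the only case it admits is "events present prior to start of the randomized treatment but increased in severity based on preferred term". The section also defines a separate class: "Pre-treatment AEs are adverse events started between ICF signature and prior to the first administration of randomized study treatment". The summaries of drug-related events, SAEs and events leading to discontinuation are then specified for treatment-emergent events only.

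SAP Section 4 opens with "The following analyses are updated and changed from protocol amendment version 1 dated 20 Apr 2021" and lists one item, the covariance structure for the SANDE model. It says nothing about the adverse event definition.

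**The concern.** The protocol does not say which of its two definitions governs the tables, and the SAP adopts one without comment. The conditions left out concern events that become serious or come to be suspected of a drug relationship. Those are the events that the SAE and drug-related tables exist to show.

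Incidence and severity of adverse events is the safety endpoint among the Part 1 secondary objectives, and protocol Section 3 starts Part 2 only if safety and efficacy are demonstrated in Part 1. A reader comparing ECF843 with vehicle in the by-treatment tables would expect these events to be there.

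A smaller gap concerns timing. Treatment-emergent means after the first administration and pre-treatment means before it. No rule covers an event for which only a date is known and that date is the day of the first randomized dose.

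**Working it through.** The documents give no figure to reproduce on this point. The check is a comparison of text, followed by tracing where an affected event ends up.

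**Step 1. Apply the three rules to the same events.** Inputs are the two definitions in protocol 12.5.2 and the rule in SAP 2.8.1.

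| Event | Protocol, introducing definition | Protocol, closing paragraph | SAP 2.8.1 |
|---|---|---|---|
| Starts on a date after the first randomized dose | counted | counted | counted |
| Present before, severity increases | counted | counted | counted |
| Present before, becomes suspected, severity unchanged | not counted | counted | not counted |
| Present before, becomes serious, severity unchanged | not counted | counted | not counted |

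The SAP agrees with the first protocol definition in every row. It differs from the second in the last two.

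**Step 2. Can those rows occur?** Protocol 10.1.1 grades severity by interference with normal activities. It records relationship to study treatment and seriousness as separate items, and 10.1.2 defines seriousness by other criteria, such as hospitalization or medical significance. An event can therefore become serious or suspected while its severity grade stays the same.

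**Step 3. Are pre-existing events plausible at the first randomized dose?** Adverse events are collected from consent onward. Protocol Section 3 says all Part 1 subjects receive vehicle at some point and caps ECF843 exposure at 28 of the 56 days. SAP 2.1.1.2 ties the reference date in Part 1 to the first dose of the treatment actually randomized. The sequence of periods cannot be seen in the public text, so this shows that such events are plausible, not how common they are.

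**Step 4. Where does such an event appear under the SAP as written?**

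- Pre-treatment summary for Part 1: yes, but as an event that began before randomized treatment.
- Drug-related and SAE summaries by treatment: no, because these are limited to treatment-emergent events.
- Death summary: SAP 2.8.2 covers all deaths, so fatal events are protected.
- Subject listings: yes, but these are not comparative tables.
- ESS1 tables: presented by TID or BID posology, so they do not separate ECF843 from vehicle. The period and membership of ESS1 are partly redacted, so coverage cannot be checked.

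**Step 5. The day of the first dose.** Protocol 10.1.1 names start and end dates and does not mention a clock time. SAP 2.1.1.2 defines the first administration as a date. If the comparison is made by date and strictly, a complete date equal to the first-dose date is neither later nor earlier, so the event is in no class. Both protocol definitions also say after, so they give no answer either. A partial start date can reach the same point: under SAP 5.1.1.2 an imputed start later than the end date is reset to the end date, which may be that day. Elsewhere the SAP does settle same-day cases. Baseline in 2.1.1.3 includes values on the first administration, and concomitant medication in 2.4.2 runs from that day.

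**The case against.** The strongest reply is that the SAP does not depart from the protocol. It follows, almost word for word, the definition that the protocol attaches to the same tables, so its silence in Section 4 is understandable. That stands: the fault is a contradiction inside protocol 12.5.2 that the SAP carries forward. It does not remove the need to settle the rule, because the wider paragraph is also current protocol text.

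A reader might infer that ECF843 adverse events are under-counted. The documents do not support that. The rules are the same for ECF843 and vehicle. The onset condition in SAP 2.8.1 has no end date, so an event starting after the last dose is both treatment-emergent and post-treatment, which raises counts. Pre-existing events remain in the pre-treatment summary and the listings. No treatment-emergent count or threshold is stated for the decision to start Part 2.

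A reader might also infer that reactions on the first dosing day are lost. As written, the SAP speaks of the administration and not its date, so a reaction after the first drop is treatment-emergent. The loss arises only if the program requires an event date later than the dose date, which the SAP does not state. The imputation rule for partial dates, "And the AE month is missing the imputed AE start date is set to the AE reference start date + 1 day", does not show otherwise. When the reference is treatment start, it generally makes the event treatment-emergent, and it says nothing about complete dates.

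Finally, SAP 5.1.1.2 leaves a missing start year as a null date. No text says that such an event is then excluded, so this is missing detail and not a demonstrated loss.

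**Conclusion.** The point holds as an unreconciled definition with a specific consequence. Followed as written, SAP 2.8.1 leaves out of the by-treatment drug-related and SAE tables any non-fatal event present at the first randomized dose that later becomes serious or suspected without a severity increase. The closing paragraph of protocol 12.5.2 would count it.

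The size cannot be computed: the documents give neither adverse event rates nor a share of events that convert in this way. Such events are likely few. The conclusion assumes that the tables are programmed from the SAP wording and that no redacted text adds the missing conditions. It does not extend to a net under-count of ECF843 events or to a bias between arms. The first-dose-day question is a clarification only.

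**What to change.** Bring the two definitions in protocol 12.5.2 and the one in SAP 2.8.1 together into a single rule. The direct way is to add to the SAP definition any pre-existing event that, after the start of randomized treatment, goes from not suspected to suspected or develops into an SAE. If the narrower rule is kept, list it in SAP Section 4 as a choice between the two protocol definitions, with the reason.

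As a clarification, state that an event dated on the day of the first randomized dose is treatment-emergent unless it is recorded as starting before dosing. The imputation rules in SAP 5.1.1.2 need no change for this.

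The cost is some SAP wording and one flag derivation. The flag has to recognize when relationship or seriousness changed; the documents do not show whether the eCRF holds that date, so the derivation should say how the change is identified. The small downside of the same-day rule is that a few events that began before dosing on that day may be counted, under the same rule in all arms.

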# 2.8.1.1 Adverse events of special interest / grouping of AEs

Not applicable.

# 2.8.2 Deaths

All deaths that occurred during the study will be summarized by system organ class, preferred term and treatment group. A subject listing will be presented for all deaths including date and cause of death.

# 2.8.3 Laboratory data

Not applicable.

# 2.8.4 Other safety data

# 2.8.4.1 Corrected Visual Acuity

Snellen visual acuity (VA) testing in each eye will be conducted. The Snellen numerator and denominator will be entered in the eCRF. ETDRS will be derived from the Snellen visual acuity for summary.

Descriptive summaries (mean, median, 25th percentile, 75th percentile, standard deviation, minimum and maximum, the number of non-missing observations, and 95% confidence interval) of change from baseline VA values will be presented at each study visit by treatment group in SAF1 and SAF2, by dosing posology (TID and BID) in ESS1.

# 2.8.4.2 Intraocular Pressure

Intraocular pressure (IOP) measurements will be recorded in mmHg and rounded to the nearest whole number for summary.

Novartis
SAP

Descriptive summaries (mean, median, 25th percentile, 75th percentile, standard deviation, minimum and maximum, the number of non-missing observations, and 95% confidence interval) of change from baseline IOP values will be presented at each study visit by treatment group in SAF1 and SAF2, by dosing posology (TID and BID) in ESS1.

#### 2.8.4.3 Slit Lamp Exam and Fundus Exam/Ophthalmoscopy

Slit lamp and Fundus exams will be performed, and results will be captured in the source document at each visit. The eCRF will record only if those assessments were indeed performed or not for compliance perspective.

A subject listing will be presented by visit.

#### 2.9 Pharmacokinetic endpoints

Not Applicable.

# 2.10 PD and PK/PD analyses

[figure not shown]
Not Applicable.

# 2.11 Patient-reported outcomes

The site personnel should check PRO measures for completeness and ask the subject to complete any missing responses. The responses that are stored electronically in the database will be considered the source file.

All observed data will be used for analysis and missing data will not be imputed. And the analysis for Part 1 and Part 2 will be based on FAS 1 and FAS 2, respectively

# 2.13 Other Exploratory analyses

The analysis of exploratory endpoints for Part 1 and Part 2 will be based on FAS 1 and FAS 2, respectively. Only observed data will be used for analysis and no missing data will be imputed.

Two interim analyses are planned for the study. The first interim analysis will be perfromed when after all subjects have completed their participation in Part 1. The data will be analyzed to determine the efficacy and safety of ECF843 vs vehicle and selection of the optimal concentration and posology.

Part 2 will be initiated only if safety and efficacy of ECF843 during Part 1 is demonstrated. The second interim analysis will be performed when all subjects in Part 2 have completed 12 weeks of treatment or discontinued treatment. The analysis will be used to explore efficacy and safety of ECF843 vs. vehicle after 12 weeks of treatment. The final analysis will be performed at the end of Part 2.

# 3 Sample size calculation

# 3.1 **Primary endpoints(s)**

Part 1 of the study is powered on 2 primary endpoints, change from baseline in SANDE symptom score and composite corneal fluorescein staining score.

#### 3.1.1 SANDE symptom scores

In one previous rhLubricin clinical study (LUB0114MD) there was an observed standard deviation of 20 mm in change from baseline of SANDE score (measured with a visual analog scale (VAS)100mm)at Day 28. A second rhLubricin clinical study (LUB0115MD) showed a standard deviation of 23 mm in change from baseline in SANDE symptom score at Day 14.

[figure not shown]
Assuming a true treatment difference in change from baseline in SANDE symptom score of 10 mm and a standard deviation of 23 mm, a sample size of 112 subjects per arm provides approximately 80% power that the primary analysis will be statistically significant at the two-sided 5% significance level adjusted by 3 comparisons.

See Table 3-1 for power to detect a significant difference from vehicle under various assumed treatment effect of SANDE Symptom score and standard deviation.

able 5-1 Tower to betect a dignificant binerence nom venicle					
		Treatment effect: difference from vehicle in change from baseline in SANDE Symptom Score			
Standard deviation of change from baseline in SANDE symptom score	10	11	12	13	14
23	80%	88%	93%	97%	98%
25	72%	81%	88%	93%	96%
27	64%	74%	82%	88%	93%

 Table 3-1
 Power to Detect a Significant Difference from Vehicle

[figure not shown]
# 3.1.2 Composite corneal fluorescein staining score

nQuery Advisor 8.4 is used for the estimate.

